#### 4.10.1.4 Interim Analyses

An interim analysis can be considered at any time but might be triggered by the following combinations of number of patients and follow-up in case of substantial recruitment or feasibility issues:

- 300 patients with 40 weeks follow-up
- 400 patients with 32 weeks follow-up
- 500 patients with 24 weeks follow-up.

The purpose of a potential interim analysis is based on recruitment/feasibility. Its purpose is to best utilize all available data collected up to these timepoints, if it is identified that enrolment is not sufficient to reach our recruitment goal by the currently targeted study end.

If performed, the appropriate type of analyses will be based on the percentage of the total number of expected patients in the cohort and what types of data are present, at the timepoint at which the interim analysis occurs. At a minimum, summary statistics for study endpoints will be provided for the overall population and by-patient population (DKD vs. non-DKD) for both the retrospective and prospective phases. Additionally, shift tables of patients to eGFR categories of retrospective and prospective phases will also be provided.

If it is observed that enrolment meets or exceeds the expected recruitment goals, then the right is reserved not to perform the above proposed interim analyses, as per the CTP.

No adjustment for controlling Type I error rate is necessary, since this study is exploratory in nature and no formal hypothesis testing is planned. Data cleaning will be performed for the interim analysis. Details of any interim analysis (in the case that an interim analysis is done) will be provided in either an addendum to this analysis plan, or an interim analysis plan.

#### 4.10.1.5 Examination of Subgroups

Where specified, some analyses will be performed separately by the following patient populations:

- Diabetic Chronic Kidney Disease (DKD) patients
- Non-diabetic Chronic Kidney Disease (non-DKD) patients.

Note that analyses other to those specified in this SAP may be performed by the DKD/non-DKD populations or other subgroups where deemed necessary.

#### 4.10.2 Primary Outcome Variable

The primary outcome is the homogeneity (eGFR slope shift table) between eGFR slopes derived from retrospective and prospective eGFR values. All analyses of the primary outcome will be done on the FAS, and percentages will be based on the number of patients in the FAS, unless otherwise specified.

Retrospective and prospective eGFR slopes will be derived using a linear random slope model. The prospective eGFR slope for each patient will be derived using eGFR values in the prospective phase as the dependent variable and time in the prospective phase (years, starting from baseline) as the continuous independent variable with random intercept and random slope. The retrospective eGFR slope for each patient will be derived similarly using the data in the retrospective phase, and time in the retrospective phase will be calculated relative to the first retrospective measurement per patient. Note that for the prospective slope, all measurements from baseline until the last available visit will be considered for inclusion in the estimation, including unscheduled visits.

The primary analysis assessing homogeneity between retrospective and prospective eGFR slopes will first be performed using the retrospective eGFR slopes collected from retrospective data, and the prospective eGFR slopes derived using prospective eGFR measurements from Mitra® samples from both at-home and clinic visits. The primary analysis will then be performed again using the retrospective eGFR slopes collected from retrospective data, and prospective eGFR slopes derived from prospective eGFR measurements from venous blood samples from clinic visits. This is in order to assess differences in the slope estimation depending on the data source.

Other than this requirement, all available patient data will be included for the estimation of the retrospective slope. However, for the prospective slope, the following additional data resulting from changes to background therapy will be excluded from the eGFR slope estimation:

- For patients on SGLT2i/ACEi/ARB background therapy at date of eGFR baseline measurement, eGFR data collected after the patient dropped out of SGLT2i/ACEi/ARB will be excluded
- For patients who are not on SGLT2i/ACEi/ARB background therapy at date of eGFR baseline measurement, eGFR data collected after the patient starts SGLT2i/ACEi/ARB will be excluded
- For patients who are on ACEi/ARB background therapy at date of eGFR baseline measurement, eGFR data occurring after a change in ACEi/ARB dose occurs will also be excluded.

If the eGFR baseline measurement in the above definition is missing, then the date of study Day 1 will be used, per the definition in section 4.2.

These background therapies will be identified via the following WHO-DD ATC codes:

Therapy Type	ATC Codes
SGLT2i	A10BK
ACEi	C09A, C09B
ARB	C09C, C09D

The linear random slope for the eGFR values  $Y_{ij}$  at time  $i$  for patient  $j$  will be estimated via a linear mixed regression model (using restricted maximum likelihood) with the following model form, assuming the  $Y_{ij}$  follow a Normal distribution

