3.3 SELECTION OF TRIAL POPULATION

The study population will consist of both diabetic chronic kidney disease (DKD) as well as non-diabetic chronic kidney disease (ndCKD). The proportion of ndCKD population required to be enrolled in the study is in the range of 33%-60%. The selected Chronic Kidney Disease population will only include approximately 33% of patients with eGFR decline at least 1 ml/min/1.73m²/year and approximately 66% of rapid progressors with eGFR decline of at least 3ml/min/1.73m²/year or 8% eGFR decline/year determined via retrospective eGFR assessments.

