3.3.2 Inclusion criteria

1. Signed and dated written informed consent in accordance with ICH-GCP and local legislation prior to admission to the trial.
2. Patients with available medical records for data abstraction to meet the objectives of the study.
3. Male or female patients aged ≥ 18 years at time of consent.
4. Body Mass Index (BMI) ≥ 18.5 and < 50 kg/m² at Visit 1.
5. Clinical diagnosis of CKD.
6. eGFR decline of at least 1ml/min/1.73m²/year based on historical data from (electronic) medical records.
7. eGFR (Chronic Kidney Disease Epidemiology Collaboration [CKD-EPI] formula) 20 – 90 ml/min/1.73m² at Visit 1 calculated from serum creatinine measured by a central laboratory.
8. Patients are expected to be on optimal and stable background treatment (according to local therapy guidelines).
9. At least 4 serum creatinine values in the retrospective phase:
 - The most recent creatinine value not more than 6 months prior to Visit 1 (Screening Visit).
 - The most recent and oldest serum creatinine values should be no less than 1 year apart and no greater than 5 years apart.
 - There should be no gap of creatinine values of 2 years or longer.

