7.5 DETERMINATION OF SAMPLE SIZE

The trial will be conducted in a cohort of 600 patients, pending feasibility and enrolment period. To obtain a good representation of subjects across eGFR slopes spectrum, 600 patients will be enrolled. The goal is to achieve 400 fast progressors with an eGFR slope ≥ 3 mL/min/1.73m²/year and 200 slow progressor patients with an eGFR slope between 1 and 3 mL/min/1.73m²/year).

The sample size determination is not based on statistical considerations, but on feasibility, and there is no formal statistical hypothesis defined in the study. However, the sample size of 600 patients is considered adequate to evaluate the homogeneity of the retro- and prospective slopes. If the true (unobserved) proportion of patients have an eGFR slope ≥ 3 mL/min/1.73m² based on retrospective data and in the prospective observed period is 70%, 600 patients will provide an estimate of the proportion of at least 67% with a probability of 95%.

On the other hand, if the true (unobserved) proportion of patients have an eGFR slope ≥ 3 mL/min/1.73m² based on retrospective data and in the prospective the observed period is 50%, 600 patients will provide an estimate of the proportion of at least 47% with a probability of 95%. Results based on these parameters would be considered less than success, i.e. that we are less likely to be able to suggest or “conclude” that the retrospective and prospective slopes are homogeneous.

8. INFORMED CONSENT, TRIAL RECORDS, DATA PROTECTION, PUBLICATION POLICY, AND ADMINISTRATIVE STRUCTURE

The trial will be carried out in compliance with the protocol, the ethical principles laid down in the Declaration of Helsinki, in accordance with the ICH Harmonized Guideline for Good Clinical Practice (GCP), relevant BI and CRO Standard Operating Procedures (SOPs), the EU directive 2001/20/EC / EU regulation 536/2014, and other relevant regulations.

Investigators and site staff must adhere to these principles. Deviation from the protocol, the principles of ICH GCP or applicable regulations as will be treated as “protocol deviation”. Standard medical care (prophylactic, diagnostic and therapeutic procedures) remains the responsibility of the treating physician of the patient.

The investigator will inform the sponsor immediately of any urgent safety measures taken to protect the trial patients against any immediate hazard, as well as of any serious breaches of the protocol or of ICH GCP.

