**Equation 1**

$$E(Y_{ij}) = a_0 + b_{0j} + (a_1 + b_{1j})T_{ij}$$

Where  $a_0$  is the fixed effect term for the common intercept (across all patients),  $b_{0j}$  is the term for the random intercept of patient  $j$  and follows a Normal distribution,  $a_1$  is the fixed effect term for the common slope (across all patients) and  $b_{1j}$  is the term for the random slope of patient  $j$  and follows a Normal distribution.  $T_{ij}$  represents the time (in years) in the phase for patient  $j$  and time  $i$ . For a given patient, the random slope quantifies the difference between the observed eGFR slope of the patient and the population-averaged (common) eGFR slope. Therefore the combination of  $a_1 + b_{1j}$  represents the eGFR slope for each patient, and will be the primary quantity of interest in this analysis. The primary analysis will come from an unadjusted model as shown above. An autoregressive covariance structure will be used in this model in the first instance, however other covariance structures may be used, especially in the case of model non-convergence. If an autoregressive covariance structure results in non-convergence, then a compound symmetry structure will be tried. In the case that neither of these covariance structures results in convergence, other structures may be tried and the final choice of covariance structure will be detailed in the output. Note that the eGFR slope resulting from Equation 1 is expected to be negative as eGFR is expected to decline over time.

[figure not shown]
The primary analysis used to evaluate homogeneity of the slopes will be a shift table of the shift in number of patients with categories of estimated eGFR slopes of  $> -1$ ,  $> -3$  to  $-1$  (slow progression) and  $\leq -3$  mL/min/1.73m^2/year (fast progression) from the retrospective phase to the prospective phase. This analysis will be presented overall and for the DKD and non-DKD populations. Percentages will be based on the number of patients within each category in the retrospective phase. This analysis will

[figure not shown]
be performed once using prospective eGFR measurements from Mitra® samples and once using prospective eGFR measurements from venous blood samples.

[figure not shown]

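### Enrolment sorts patients by their own recorded decline, but the primary shift table sorts them by model slopes shrunk toward the cohort mean, so some patients enrolled as slow may be analysed as fast

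*SAP*

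**What the plan says.** **Enrolment.** Criterion 6 (Protocol 3.3.2) requires "eGFR decline of at least 1ml/min/1.73m²/year based on historical data from (electronic) medical records". Protocol 7.5 sets the mix: "The goal is to achieve 400 fast progressors with an eGFR slope" of at least 3 mL/min/1.73m²/year, and "200 slow progressor patients with an eGFR slope between 1 and 3". Protocol 3.3 gives a second route into the rapid group: "or 8% eGFR decline/year determined via retrospective eGFR assessments". The formula used at screening is not stated. It cannot be the whole-cohort model, because the cohort does not exist when a patient is screened.

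**Analysis.** SAP 4.10.2 says "Retrospective and prospective eGFR slopes will be derived using a linear random slope model", and for the earlier phase "The retrospective eGFR slope for each patient will be derived similarly using the data in the retrospective phase". Under Equation 1, the common slope plus the patient's random slope "represents the eGFR slope for each patient, and will be the primary quantity of interest in this analysis". The shift table cuts this quantity at -1 and -3. On denominators: "Percentages will be based on the number of patients within each category in the retrospective phase". An autoregressive covariance is tried first and compound symmetry second. The SAP does not say whether these describe the random effects or the residuals.

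No visible section links the category at enrolment to the category in the table. I use the SAP's sign below, so fast means a slope of -3 or lower.

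**The concern.** Two slope definitions feed one comparison. A predicted random slope is a weighted average of the patient's own slope and the cohort mean, and the patient's weight falls as the record gets shorter or noisier. Criterion 9 admits records as thin as 4 values over 1 year. If the cohort mean lies beyond -3, the pull carries patients enrolled as slow across the cut, and few or none move back.

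The rows and denominators of the only primary outcome would then differ from the groups that were recruited, and no visible table would show it. If the prospective mean also lies beyond -3, both sets of predictions crowd into the fast-fast cell. Agreement can then reflect the shared pull rather than stable individual decline.

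**Working it through.** **1. The plan's own figure.** Protocol 7.5 and SAP 4.12 say that 600 patients give an observed proportion of at least 67% (true 70%) or 47% (true 50%) with probability 95%. Exact binomial: P(X ≥ 402 | 600, 0.70) = 0.949 and P(X ≥ 282 | 600, 0.50) = 0.935. Both are within 2 points of 95%. The statement covers sampling error only and takes each patient's category as given.

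**2. Where the mean lies.** With 400 fast patients (average slope f) and 200 slow patients (average s), the mean is (2f + s)/3. It is below -3 when f < (-9 - s)/2. If s = -2, that means f < -3.5. This is likely but not certain. In the simulations of step 6 with separate variances, the fitted common slope was -3.6 to -5.4.

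**3. Effect of shrinkage.** With cohort mean m and reliability L, an own slope s becomes m + L(s - m). It is classed fast when s ≤ m + (-3 - m)/L. If slow slopes are uniform on -3 to -1, the share moved is [(1 - L)/L] × (|m| - 3)/2. With m = -4.5 (assumed):

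| L | 0.9 | 0.8 | 0.7 | 0.6 | 0.5 |
|---|---|---|---|---|---|
| Slow analysed as fast | 8% | 19% | 32% | 50% | 75% |

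**4. Sparsest eligible record.** Four equally spaced values over 1 year give a sum of squares in time of 0.556. With slope SD 3 and residual SD 4 (assumed), L = 9/(9 + 16/0.556) = 0.24. With m = -4, the own slope needed to be classed slow is -4 + 1/0.238 = +0.2, which criterion 6 excludes.

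**5. The covariance structure changes this.** If the autoregressive structure is placed on the random effects, intercept and slope share one variance, and the intercept dominates it. The fitted common SD was about 10.5 with a simulated intercept SD of 15. The record in step 4 then has L = 110.25/(110.25 + 28.8) = 0.79 and a threshold of -4 + 1/0.793 = -2.74. About 0.26/2 = 13% of a uniform slow group would move (ignoring the intercept-slope correlation). For two random effects, compound symmetry is the same matrix, so the SAP's fallback would change nothing.

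**6. Simulation.** Cohorts of 400 fast and 200 slow patients were selected on own least-squares slope, fitted by REML and re-classified. Assumed, because the documents give none of it: source slope mean and SD of (-2, 2), (-3, 3) or (-3, 4); residual SD 2, 4 or 6; intercept SD 15; independent residuals.

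| Values, span | Separate variances: slow to fast | Common variance: slow to fast | Common variance: fast to slow |
|---|---|---|---|
| 4-6, 1-3 years | 28-100% | 3-42% | 1-13% |
| 4-12, 1-5 years | 11-99% | 1-23% | 1-11% |
| 10-20, 3-5 years | 3-55% | 1-10% | 0-7% |

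With separate variances, fast to slow was 0% throughout. For 4-12 values over 1-5 years at residual SD 4, slow to fast was 36-54% with separate variances and 8-10% with a common variance. Further cohorts with exactly 4 values over 1 year (source mean -3, slope SD 3, residual SD 3-4) gave 100% and 39-45%, with 5-9% of fast patients moving back under the common variance. The structure on the residuals was not fitted. If the true residuals are independent, it should behave much like separate variances.

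**7. Is the re-sorting wrong?** Not all of it. With separate variances, 7-46% of enrolled-slow patients had a true slope of -3 or lower.

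**8. Agreement.** In a sparse-record run with separate variances, agreement between phases was 72% on model slopes and 59% on own slopes. Agreement of the category with the true slope was 58% and 70%. These figures are illustrative. The inflation needs a prospective mean that is also beyond -3, and it can disappear or reverse otherwise.

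**9. The 8% route.** 3/0.08 = 37.5, so below eGFR 37.5 an 8% yearly decline is less than 3 (1.6 at eGFR 20). Such a patient is enrolled as rapid and can be analysed as slow, which runs against the main drift.

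**The case against.** The protocol itself specifies the random-slope model for both phases (7.2.2), and its aim is homogeneity of slopes. Protocol 8.5.2 plans to find fast progressors for Phase III with a mixed model, so a model slope is a reasonable primary quantity. This stands, and it is why the model table should remain primary. That later model would use a different database, however, and so a different shrinkage target. A category found here need not carry over.

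The SAP revision history records a change from unstructured to autoregressive covariance in version 2.0. The largest shares above use separate variances, so they describe the current plan only if the autoregressive structure belongs to the residuals. This stands too.

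A reader might infer that a large part of the slow group will be analysed as fast, or that the slow row will be emptied. The documents do not support that. They give no residual SD, slope SD, record density or screening formula, and in the common-variance simulations the slow row was never emptied. A reader might also infer that statements about selecting fast progressors should rest on own slopes alone. Nor is that supported: own slopes are noisier for short records, and least squares at screening is an assumption.

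Finally, the study is exploratory, the 400/200 split is a goal, and the study was terminated in July 2022 (SAP 3.1.1.1), so the split may not have been reached. The same section still requires all planned analyses. The supportive section 4.10.2.2 is not visible and may already hold a sensitivity table.

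**Conclusion.** The mismatch between the enrolment slope and the analysis slope follows from the documents. The direction of the drift follows from the 2:1 goal, provided the cohort mean lies beyond -3. The size is not known. Under the assumptions shown, about 3-100% of enrolled-slow patients are analysed as fast with separate intercept and slope variances, with no fast patient moving back in the simulations. With the autoregressive structure on the random effects the range is about 1-45%, with 0-13% of fast patients moving back. Within each range, record density and residual variance decide. Some of the movement corrects enrolment error, and the 8% route works the other way. As planned, the primary table cannot show how far its rows differ from the recruited groups, or how much of its agreement comes from shrinkage. This is a cheap improvement to the plan and does not invalidate the primary analysis.

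**What to change.** Keep the model-based shift table as primary. In SAP 4.10.2 add:

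1. A sensitivity shift table whose retrospective rows use each patient's own least-squares slope, overall and by DKD status.
2. A cross-table of the category recorded at enrolment, with patients entered by the 8% route shown separately, against the model-based retrospective category. A footnote should say how the enrolment slope was calculated.
3. A statement of whether the autoregressive structure, and its compound-symmetry fallback, applies to the random effects or to the residuals.

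Interpret homogeneity, and any statement about selecting fast progressors, from the model-based and own-slope shift tables together.

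The cost is some SAP wording and two tables from data already held. If the enrolment category was not recorded, the SAP should say so. The drawback is that own slopes are noisier for short records, so the sensitivity table will show some movement that is only measurement error.
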